8.1 Definitions

Unanticipated Problems Involving Risk to Subjects or Others

Any incident, experience, or outcome that meets all of the following criteria:

- Unexpected in nature, severity, or frequency (i.e. not described in study-related documents such as the IRB-approved protocol or consent form, the investigators brochure, etc)
- Related or possibly related to participation in the research (i.e. possibly related means there is a reasonable possibility that the incident experience, or outcome may have been caused by the procedures involved in the research,
- Serious (as defined below) “Serious” is different than “severe” as reported in the CTC criteria that applies a grade to the AE.

Adverse Event

An **adverse event** (AE) is any symptom, sign, illness or experience that develops or worsens in severity during the course of the study. Intercurrent illnesses or injuries should be regarded as adverse events. Abnormal results of diagnostic procedures are considered to be adverse events if the abnormality:

- results in study withdrawal
- is associated with a serious adverse event
- is associated with clinical signs or symptoms
- leads to additional treatment or to further diagnostic tests
- is considered by the investigator to be of clinical significance

Serious Adverse Event

Adverse events are classified as serious or non-serious. A **serious adverse event** is any AE that is:

- fatal
- life-threatening
- requires or prolongs hospital stay
- results in persistent or significant disability or incapacity
- a congenital anomaly or birth defect
- an important medical event

Important medical events are those that may not be immediately life threatening, but are clearly of major clinical significance. They may jeopardize the subject, and may require intervention to prevent one of the other serious outcomes noted above. For example, drug overdose or abuse, a seizure that did not result in in-patient hospitalization, or intensive treatment of bronchospasm in an emergency department would typically be considered serious.

All adverse events that do not meet any of the criteria for serious should be regarded as **non-serious adverse events**.

Adverse Event Reporting Period

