8.3.2 Investigator reporting

For reportable deaths, the initial submission to the UNC IRB may be made by contacting the IRB Director or Associate Director. The AE/Unanticipated Problem Form is required as a follow up to the initial submission.

Other Reportable events:

For clinical drug trials, the following events are also reportable to the UNC IRB:

- Any adverse experience that, even without detailed analysis, represents a serious unexpected adverse event that is rare in the absence of drug exposure (such as agranulocytosis, hepatic necrosis, Stevens-Johnson syndrome).
- Any adverse event that would cause the investigator to modify the investigators brochure, protocol or informed consent form, or would prompt other action by the IRB to assure protection of human subjects.
- Information that indicates a change to the risks or potential benefits of the research, in terms of severity or frequency. For example:
 - An interim analysis indicates that participants have a lower rate of response to treatment than initially expected.
 - Safety monitoring indicates that a particular side effect is more severe, or more frequent than initially expected.

- A paper is published from another study that shows that an arm of your research study is of no therapeutic value.
- Change in FDA safety labeling or withdrawal from marketing of a drug, device, or biologic used in a research protocol.
- Breach of confidentiality
- Change to the protocol taken without prior IRB review to eliminate apparent immediate hazard to a research participant.
- Incarceration of a participant when the research was not previously approved under Subpart C and the investigator believes it is in the best interest of the subject to remain on the study.
- Complaint of a participant when the complaint indicates unexpected risks or the complaint cannot be resolved by the research team.
- Protocol violation (meaning an accidental or unintentional deviation from the IRB approved protocol) that in the opinion of the investigator placed one or more participants at increased risk, or affects the rights or welfare of subjects.

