3. Adverse events will be reported to the UNC-CH IRB and to the NIH as required. Following UNC-CH Adverse Event guidelines, events that meet the criteria for an unanticipated problems involving risks to subjects or others (UPIRSO) and are also serious adverse events will be reported to the IRB within one (1) week of the investigator becoming aware of the event. Any other events that meet the criteria for a UPIRSO will be reported to the IRB within two (2) weeks of the investigator becoming aware of the problem. In accordance with the terms of the Federal Wide Assurance, the Office for Human Research Protections (OHRP) and the Federal Drug Administration (FDA) are notified in a timely manner of 1) serious or continuing noncompliance; 2) significant adverse events involving risk to participants or others; or 3) suspension or termination of IRB approval for a study. Unexpected problems involving risk, unless the event is serious and related to the research, are not routinely submitted to the sponsor.
4. Adverse events will be identified through clinical interviews, laboratory results, safety tests, and self-report questionnaires.
5. Every event will be reported to the principal investigator and [name] by the designated research associates and will be documented. An adverse event report will be generated for each even and will include a description of the event, when and how it was reported, and any official chart records or documentation to corroborate the event.
6. The adverse event report will also include the severity attribution of the adverse event using the Common Toxicity Criteria (CTC) scale: 0 = no adverse event or within normal limits; 1 = mild AE, not requiring treatment; 2 = moderate AE, resolved with treatment; 3 = severe AE, resulted in inability to carry on normal activities and required professional medical attention; 4 = life threatening or disabling AE; 5 = fatal AE.
7. The adverse event report will also include a determination of attribution according to the following scale: 0 = definitely not related; 1 = probably not related; 2 = possibly related; 3 = probably related; 4 = definitely related.

III. Safety Review Plan and Monitoring

Oversight of participant safety includes a review of adverse events as well as study progress, data integrity, and study outcomes.

A. Justification of sample size

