We will have 80% power to detect a large effect size (.7) in 20 women. Our recently completed study of the effects of transdermal estradiol on mood symptoms in the same population showed a reduction in depressive symptoms with the PM-MDD group from pre-treatment to post-treatment ($t=4.3$, $p<0.001$ Cohen's $d=1.15$). We anticipate the TSEC (the active ingredient of which is estrogen) to have similar effects on mood symptoms, and thus, the sample size of 20 is a conservative estimate of the number of subject we will need to detect a statistically significant effect.

B. Safety and study progress reviews

1. The research coordinator will evaluate the study subjects at appropriate intervals and assess laboratory data and clinical signs for potential adverse events. The research coordinator will assist the PI with gathering information to help the PI determine classification and causality. The research coordinator will also observe and document all adverse events, act on the PI's recommendation, and maintain follow-up until reconciliation.
2. The principal investigator and [name] will review the adverse events, immediately after they occur, with follow-up resolution. The principal investigator and [name] will evaluate individual and cumulative participant data when making recommendations regarding the safe continuation of the study. The principal investigator will be notified within 24 hours of an adverse event.
3. Specific responsibilities of the principal investigator include:
 - a. Review the research protocol, informed consent documents, and plans for data safety and monitoring;
 - b. Evaluate the progress of the trial, including periodic assessments of data quality and timeliness, participant recruitment, accrual and retention, participant risk versus benefit, performance of the trial site, and other factors that can affect study outcome;
 - c. Consider factors external to the study when relevant information becomes available, such as scientific or therapeutic developments that may have an impact on the safety of the participants or the ethics of the trial;
 - d. Protect the safety of the study participants;
 - e. Report on the safety and progress of the trial;
 - f. Make recommendations to the UNC-CH IRB, and, if required to the Food and Drug Administration (FDA) concerning continuation, termination, or other modifications of the trial based on the observed beneficial or adverse effects of the treatment under study;

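### Grade 2 of the adverse-event severity scale requires the event to have resolved with treatment, so moderate events that are untreated or still ongoing fit no grade

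*Combined protocol and SAP*

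**What the plan says.** Appendix A, II.B item 6 makes the grade a required part of each report: "The adverse event report will also include the severity attribution of the adverse event using the Common Toxicity Criteria (CTC) scale". Grades 2 and 3 are "2 = moderate AE, resolved with treatment; 3 = severe AE, resulted in inability to carry on normal activities and required professional medical attention". Grade 1 is a mild event for which treatment is not required, and grade 4 is one that threatens life or is disabling, with 0 for no event and 5 for a fatal one.

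The main protocol offers no other severity definitions. Section 8.1 mentions CTC grading only to distinguish *serious* from *severe*.

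On timing, Section 8.2 has every event entered in the source document at once and then followed until it resolves or stabilizes. Appendix A, III.B says the principal investigator and one other named person "will review the adverse events, immediately after they occur, with follow-up resolution", and adds: "The principal investigator will be notified within 24 hours of an adverse event". The same section has them weigh individual and cumulative data when advising on safe continuation, and calls for an annual report that lists and summarizes adverse events. No text gives a deadline for assigning the grade, or says whether it may be changed later.

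**The concern.** A severity grade should describe how bad an event is. Grade 2 also asks whether the event was treated and whether it has gone away. A moderate event that nobody treats, or that is treated and persists, does not match it. Grade 1 is confined to mild events and grade 3 to severe ones, so neither takes it in.

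Timing adds to the difficulty. Resolution is often unknown when an event is first recorded and reviewed, so grade 2 often cannot be given at that point. The plan foresees ongoing events: Section 4.4.1 anticipates side effects such as nausea or fluid retention for which relief may not be achieved. If such an event is moderate and persists, it has no grade, whether or not its management counts as treatment.

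What is at stake is the completeness and consistency of the severity column in the reports, and of whatever the cumulative review and annual report draw from it. In a single-arm study of 20 women, a few events left blank or moved up or down a grade could alter a severity summary.

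**Working it through.** The plan states no figure on this point, so there is none to reproduce. The check applies the printed definitions to every combination of three features.

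Inputs, all from Appendix A, II.B item 6:
- Intensity: mild, moderate or severe (the opening words of grades 1, 2 and 3).
- Treatment: given or not (grade 2).
- Status when graded: resolved or ongoing (grade 2).

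Number of combinations: 3 × 2 × 2 = 12.

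Reading rules:
- Grade 1 concerns whether treatment was *required*. A mild event treated without needing it stays in grade 1.
- Grade 3 likewise concerns attention being *required*. Severe events are taken to meet both of its added clauses.
- Grade 2 is different. It says the event *resolved with* treatment, so treatment must have been given and the event must be over.

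| Intensity | Untreated, ongoing | Untreated, resolved | Treated, ongoing | Treated, resolved |
|---|---|---|---|---|
| Mild | 1 | 1 | 1 | 1 |
| Moderate | none | none | none | 2 |
| Severe | 3 | 3 | 3 | 3 |

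Combinations with a grade: 4 + 1 + 4 = 9. Combinations without: 12 − 9 = 3, which is 3 of the 4 moderate ones and 3/12 = 25% of all. These are counts of categories, not of events.

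Setting the timing texts beside this: recording is immediate (Section 8.2), review is immediate and notification is within 24 hours (Appendix A, III.B). Follow-up continues to resolution or stabilization, but no text carries what is learned then back into the grade.

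**The case against.** The strongest reply is that a sensible rater will cope. Grades 1 to 3 each open with an intensity word, and a rater can grade on that alone. No deadline is set for the grade and events are followed up, so it could be completed later. One site, with the same two people reviewing every event, limits inconsistency. Section 8.3 already lists current status among the items for a narrative report. The scale is labelled as the Common Toxicity Criteria and may abbreviate a fuller source, which cannot be checked here.

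Much of this stands and keeps the point small. But the plan authorizes neither workaround. The Section 8.3 list covers only reportable serious events and unanticipated problems. The printed wording is what staff have to apply.

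A reader might infer more than the documents support:
- *A larger gap.* Counting mild treated events as ungraded adds 2 combinations (3 + 2 = 5 of 12). Counting severe events without medical attention adds 2 more (5 + 2 = 7 of 12). Both additions read *required* as *received*, which grades 1 and 3 do not say.
- *That such events are common.* Appendix A names nausea as the most common side effect, but gives no rates by severity, treatment or resolution.
- *That worsening mood treated with conventional medication is a case in point.* Section 8.5 and Appendix A, III.C already class those symptoms as severe, so they are not moderate events.
- *That the gap disables a reporting trigger.* Section 8.1 refers to events "Unexpected in nature, severity, or frequency", and Section 8.3.2 makes it reportable when "Safety monitoring indicates that a particular side effect is more severe, or more frequent than initially expected". Neither ties that judgement to the CTC grade, and no expected grade is given for any side effect.

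**Conclusion.** The point holds in a narrow form. Grade 2, as printed, leaves 3 of 12 combinations without a grade: moderate untreated ongoing, moderate untreated resolved, and moderate treated ongoing. This rests on a literal reading of item 6 and on the absence of any rule for revising a grade.

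The practical effect is modest. Section 3.4 names no primary safety endpoint. The individual stopping rule in Section 8.5 and Appendix A, III.C rests on the HRSD and the participant's own concerns. IRB deadlines in Section 8.3.1 and Appendix A, II.B item 3 depend on seriousness and unanticipated-problem status. What remains exposed is the grade in the adverse-event reports and its use in cumulative review and the annual summary. How many events would be affected cannot be estimated from the documents. This is a worthwhile low-cost correction, and does not threaten the trial's conclusions.

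**What to change.** Reword Appendix A, II.B item 6 so that grades 1 to 3 rest only on intensity and effect on normal activities: mild, no interference; moderate, some interference; severe, unable to carry on normal activities. Keep grades 4 and 5. Record treatment given, and outcome (resolved or ongoing), as two separate fields on the adverse-event report. State that the grade is assigned at onset and updated if intensity changes. While rewording, add a phrase separating grade 3 from *disabling* in grade 4, since the two can overlap.

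The cost is one reworded item and two form fields, with no added visits or staff. The downside is that the wording would depart from the scale as now printed, so the reference to the CTC scale should say that the definitions are adapted. No dose, treatment or stopping rule is affected.
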